## 7.4 Patient Numbering

Patients who have signed the informed consent form to begin screening procedures will be assigned a Subject Identification Number at that time. The participant will keep the same number throughout the study (a separate randomization number will not be provided).

#### 7.5 Randomization

To achieve balanced patient groups, subjects will be randomly assigned on a 1:1 basis in a blinded fashion to the 8-week Flicker exposure or the 4-week Flicker exposure, stratified based on gender, and age.

#### 8. STUDY ASSESSMENTS AND PROCEDURES

The study design and assessment schedule are presented in Table 1.

**8.1 Informed Consent.** The study will be discussed with the study subject and appropriate others (family, study partner) and if they are interested in learning more about the study they will be provided with a copy of the informed consent form to review in detail. The potential participant will be contacted at a later date to determine if they would like to be screened for possible study inclusion. If they are interested, a screening visit will be scheduled. Potential subjects are encouraged to discuss participation in this study with their family prior to screening for the study. In addition, they are encouraged to contact the office with any questions or concerns.

At the time of the screening visit, the consent form will be reviewed with the study subject and appropriate others, and all questions will be answered. Ample opportunity will be given for questions. If they are still interested in participating once all questions are answered to participant and study partner satisfaction, the consent is signed.

This study includes subjects who must score between >15 on the MoCA (Montreal Cognitive Assessment) and will therefore be experiencing mild cognitive impairment as a result of suspected prodromal Alzheimer's disease. Individuals with mild impairment will likely be able to provide informed consent. Capacity for consent will be determined by the study subject's ability to engage in a discussion regarding the study and their ability to understand what will be involved in study participation. The individual obtaining consent will review and discuss the research project and the consent document with the potential study participant and their family/study partner/legally authorized representative and will decide if they are able to understand the nature of the research, appreciate the experimental nature of the study, and understand the potential risks as well as alternatives to study participation.

In the event that the subject is not competent to provide consent, assent is obtained. A study subject's legally authorized representative will be present during the initial consenting process. Signed consent will be obtained from all participants and their study partners. The same process described previously will be employed in obtaining legally authorized

representative's consent, when deemed necessary. Consent will be obtained prior to conducting any screening assessments or procedures.

Participants under consideration for participation will have a diagnosis of MCI through the cognitive clinic or through consensus diagnosis as a participant in another of our research studies. Those who do not meet criteria for amnestic MCI will not be considered for participation.

## 8.2 Screening Visits. Screening Visit 1a:

- Subjects will sign a written informed consent prior to any study-related procedures.
- Medical history, including review of medications
- Physical and neurologic exams
- Vital signs, including: blood pressure, heart rate, respiratory rate, temperature
- Height and weight
- Sensory function (see/hear)
- Cognitive Testing Montreal Cognitive Assessment (MoCA)
- Flicker Tolerance Testing
- EEG
  - Flicker entrainment and exposure titration
- MR Imaging
  - If imaging is available within 6 months of screening visit 1a (including an arterial spin labeling [ASL] sequence), the screening MRI may not be performed

Screening visit 1a may take place on more than 1 day (e.g., MRI scan occurs on separate day). Subjects cleared for continued participation will undergo the following procedures at the second screening (**1b**). The tasks below may be performed on the same day, or may be performed on separate days. Screening 1b will occur within one calendar month of screening 1a.

## **Screening Visit 1b:**

- Blood work
  - Inflammatory biomarkers
  - Metabolomics
  - Primary Panel for Inflammation, Oxidative, and Nitrosative Stress
  - APOE status (if unknown)
- Retinal Imaging
- If the subject has had a clinic or research LP within 6 months prior to visit 1b and CSF has been banked, no screening LP will be performed. The banked CSF will be used for analysis. In all other cases, an LP will be performed by an MD or NP following an overnight (no less than 6-hr) fast. CSF will be assessed for the following:

- Aβ42, tau, phospho tau
- Inflammatory Biomarkers
- Contact subject on the day after LP to inquire about any adverse events.

8.3 Baseline Visits. The baseline visit will occur within 1 calendar month of Screening visit1b. Patients that continue to meet eligibility requirements will undergo the following at visit2a.

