## 4. EXPERIMENTAL DESIGN AND METHODS

4.1 Overview: For this 9-week study, 10 subjects with mild cognitive impairment (amnestic or multi-domain subtypes) will be randomly assigned to two study arms. Although all participants will receive Flicker exposure, half of the participants will receive the exposure (driving gamma) during the entire study period (8 weeks of Flicker) while the other half of the participants will receive Flicker exposure for half of the study period (2nd 4-weeks). During the 9-week course of the study, participants will undergo venous blood draws and lumbar puncture for biomarker analyses at baseline, midpoint and at 9 weeks. At the study week 4 time point, the participants currently undergoing Flicker exposure will continue with their sessions while at week 4, those initially randomized to non-exposure will initiate Flicker exposure. The primary goals are to measure safety and FLICKER tolerance while verifying the intended response. Secondary objectives include monitoring possible effects of Flicker exposure on clinical findings and biomarkers of AD progression, including CSF amyloid, tau, and phospho-tau, and volumetric MRI, as well as PET (florbetapir) and arterial spin labeling MRI and retinal amyloid changes.

**4.2 Sample Size and Power.** This is a pilot study designed to assess feasibility and tolerability in the patient population. Although the sample size of 10 subjects will allow us to make certain claims about tolerability, we do not anticipate generating clinically meaningful,

broadly applicable results from this data. Thus, our sample size is driven by the need to collect pilot data that will position us to develop a clinical trial, if warranted, based on the technology described here.

- **4.3 Flicker tolerance to date.** For studies conducted to date by Cognito Therapeutics, a total of 17 participants have undergone daily periods of sensory stimulation for up to one hour (the study paradigm planned for this work). These subjects include young adults, older adults, and older adults with cognitive impairments. These studies have helped establish the feasibility of sensory stimulation with regards to safety, comfort, and tolerability of the exposure in patients with mild-to-moderate cognitive impairments. No device or exposure-related adverse events have been reported during this study.

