## **Midpoint Visit b:**

- LP
- MRI

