## **End of Study Visit b:**

- Retinal Imaging
- Lumbar puncture

**8.5 Assessments:** MCI will be assessed using raters blinded to the study design. The cognitive battery will consist of: MoCA, CDR-SB and the Geriatric Depression Scale to help determine subject eligibility.

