## 8.8 Schedule of Assessments

On the following pages, the schedule of assessments for both treatment groups is presented.

Table 1. Schedule of Assessments for the Non-Exposure Phase/Flicker Exposure Phase

Visit Number	1a	1b	2a	2b	3	4	5	6a 	6b	7	8	9	10	11a 	11b
Study Week	Screening 		Baseline 		1	2	3	44	44	5	6	7	8	94	94
Consent	X														
Confirm eligibility	X			X											
Medical history and medication review	X							X						X	
Physical exam and neurological exam	X			X				X						X	
Vital signs + height + weight	X			X											
Sensory function (see/hear)	X							X							
APOE genotyping		X													
Blood for biomarkers		X							X						X
Cognitive assessments	X			X				X						X	
Retinal imaging		X							X						X
MR imaging	$X^5$		$X^5$					$X^3$	$X^3$					X	
Lumbar puncture		X							X						X
PET Scan			X					X						X	
Eye tracking				X				X						X	
EEG evaluation and induced activity	$X^6$			X				X						X	
Tolerance Testing	X							X						X	
Randomization/Study crossover				X				X							
Therapy training									X						
In-home observation visit										X					
In-home therapy										X	X	X	X		
Telephone call / email contact					X	X	X			X	X	X	X		X
Remote adherence monitoring										X	X	X	X		
Assessment of adverse events				X	X	X	X	X		X	X	X	X	X	

<sup>1Crossover visit (2-day visit) End of treatment visit (2-day visit)

<sup>3MRI will occur on either study visit 6a or 6b

<sup>4Study visits may extend over several days, depending on scheduling constraints

<sup>5MRI will be done at visit 1a if not done within the past 2 yrs or at 2a if done within the past 6 months

<sup>6Screening EEG may be repeated if entrainment criteria are not met or data are unreliable in subjects who have met all other eligibility criteria.

Table 2. Schedule of Assessments for the Flicker Exposure/Flicker Exposure Phase

Visit Number	la .	1b	2a	2b	3	4	5	6	7a 	7b	8	9	10	$11a^2$	11b
Study Week	Screening 		Baseline 		1	2	3	4	5 	5 	6	7	8	94	94
Consent	X														
Confirm eligibility	X			X											
Medical history and medication review	X								X					X	
Physical exam and neurological exam	X			X					X					X	
Vital signs + height + weight	X			X											
Sensory function (see/hear)	X								X						
APOE genotyping		X													

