Blood for biomarkers		X								X					X
Cognitive assessments	X			X					X					X	
Retinal imaging		X								X					X
MR imaging	X 		X 						$X^3$	$X^3$				X	
Lumbar puncture		X								X					X
PET Scan			X						X					X	
Eye tracking				X					X					X	
EEG evaluation and induced activity	$X^6$			X					X					X	
Tolerance testing	X			X					X					X	
Randomization				X											
Therapy training				X											
In-home observation visit					X										
In-home therapy					X	X	X	X	X	X	X	X	X		X
Telephone call / email contact					X	X	X	X			X	X	X		
Remote adherence monitoring					X	X	X	X	X	X	X	X	X		
Assessment of adverse events				X	X	X	X	X	X		X	X	X	X	

<sup>1Midpoint clinic visit (2-day visit)

<sup>2End of treatment visit (2-day visit)

<sup>3MRI will occur on either study visit 7a or 7b

<sup>4Study visits may extend over several days, depending on scheduling constraints

<sup>5MRI will be done at visit 1a if not done within the past 2 yrs or at 2a if done within the past 6 months

<sup>6Screening EEG may be repeated if entrainment criteria are not met or data are unreliable in subjects who have met all other eligibility criteria.

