#### 10. ASSAY MEASURES AND ANALYSES

**10.1Genotyping** for apolipoprotein E4 allele status will be performed in the Emory Genetics Core facility. Apolipoprotein E4 allele status will not be disclosed to study participants.

**10.2 EEG.** We will measure electrical brain activity using EEG from the scalp. For the EEG recording session, a cap (similar to a swim cap) will be placed on the participant's head and electrodes attached. Gel will be placed on the hair/head so that the electrodes can get a good connection to detect electrical charges that come from brain activity. This gel is easily removed with hair washing.

During the EEG study session, you will be seated in a chair. You will be asked to rest quietly with your eyes open. EEG will be recorded before, during and after use of the Flicker device (Figure 3). When the Flicker device is not in place, participants may be asked to perform simple movements, to perform a computer/iPad-based task with button presses, and/or to complete mood and cognitive assessment questionnaires.

19

Protocol: v07

There are no known risks of EEG. The gel in the hair can be sticky but is easily removed with shampooing. The EEG session may last up to 3 hours total time (including electrode placement and recording time) and will occur at 3 time points during the study: baseline, midpoint, and end-of-study.

EEG evaluation will be performed at Visits 1a and 2b for both groups to determine whether it is possible to entrain the gamma waves. If subjects' brain waves are unable to become entrained, they will be removed from the study. Screening EEG may be repeated if entrainment criteria are not met or data are unreliable in subjects who have met all other eligibility criteria.

**10.3 Lumbar Puncture (LP):** Lumbar puncture will be performed by a qualified clinician trained to perform the procedure. 20ml of CSF is collected using sterile technique and will be assayed for both known and novel biomarkers of disease, including inflammatory markers. Lumbar punctures will occur at the three in-person clinic visits (screening, midpoint, and end of study).

**10.4 CSF and Serum Biomarkers.** AD biomarkers including Aß42, tau, and phospho-tau levels in the CSF will be assayed at baseline, midpoint, and end of study visits. Specialty assays for inflammatory markers will also be conducted via a commercial vendor with specialized panels for measuring these markers (OLink, Sweden). Results are not disclosed to participants.

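### No main-phase adverse event assessment is scheduled after the final lumbar puncture, and the day-after contact is written only for the screening puncture

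*Combined protocol and SAP*

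**What the plan says.** Section 10.3 sets the number of punctures: "Lumbar punctures will occur at the three in-person clinic visits (screening, midpoint, and end of study"). In the schedules of Section 8.8 these fall at 1b, 6b and 11b in the arm that starts Flicker in the second half (Table 1), and at 1b, 7b and 11b in the arm exposed throughout (Table 2).

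Follow-up after a puncture is written once, in the list for Screening Visit 1b: "Contact subject on the day after LP to inquire about any adverse events". The list for "Midpoint Visit b" holds the LP and the MRI and nothing on AEs. The list for End of Study Visit b holds retinal imaging and "Lumbar puncture", again with nothing on AEs. The end-of-study AE review is listed under Visit a.

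The screening puncture can be waived: "If the subject has had a clinic or research LP within 6 months prior to visit 1b and CSF has been banked, no screening LP" is then done, and the stored sample is used.

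On purpose, Aim 1 (Section 2.1) covers safety, tolerability and compliance and undertakes to record any AE. Section 4.1 counts safety among the primary goals. Section 4.2 says: "Although the sample size of 10 subjects will allow us to make certain claims about tolerability".

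**The concern.** A call the day after a puncture is the protocol's own safeguard, yet it is attached to one puncture of three. At the end of the main phase the order of visits makes this matter: the AE review comes first and the invasive procedure second, so a team that follows the schedule exactly never has to ask about events after the final LP.

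This is a pilot with no powered efficacy comparison, so its AE record is one of its main products. The midpoint raises a smaller issue. In Table 1 the puncture is at 6b and in-home Flicker starts at visit 7. An event caused by that puncture may first be asked about once Flicker has begun, which makes attribution harder.

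**Working it through.** The documents give no AE rate, AE analysis or power figure on this point, so there is no stated figure to reproduce. The check is a comparison of visits, followed by an illustration under assumed rates.

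**Step 1. Order of LPs and AE assessments (Section 8.8).** The row "Assessment of adverse events" was read against the lumbar puncture and telephone rows.

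| | Table 1 | Table 2 |
|---|---|---|
| LP | 1b, 6b, 11b | 1b, 7b, 11b |
| AE assessment | 2b, 3, 4, 5, 6a, 7, 8, 9, 10, 11a | 2b, 3, 4, 5, 6, 7a, 8, 9, 10, 11a |
| Telephone/email | 3, 4, 5, 7, 8, 9, 10, 11b | 3, 4, 5, 6, 8, 9, 10 |
| In-home therapy | 7, 8, 9, 10 | 3, 4, 5, 6, 7a, 7b, 8, 9, 10, 11b |

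**Step 2. Next scheduled AE enquiry after each LP.**

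- Screening LP (1b): the day-after contact in the text, then 2b.
- Midpoint LP (6b or 7b): visit 7 (Table 1) or visit 8 (Table 2), each in the following study week. Only the prompt contact is absent.
- Final LP (11b): none marked in the main phase. The first later AE mark is at Visit 12 in Table 3, which applies only to participants who consent to the extension.

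Per participant with all three LPs, 2 of 3 are followed by a main-phase AE assessment and 1 of 3 by a day-after contact.

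**Step 3. How many LPs are uncovered.** Inputs: 10 participants allocated 1:1, so 5 per arm, all assumed to reach 11b.

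- Total main-phase LPs: 10 × 3 = 30 if every screening LP is done, and 10 × 2 = 20 if all are replaced by banked CSF.
- If Table 1's 11b mark in the row "Telephone call / email contact" does not include AE questions: 10 final LPs uncovered, which is 10/30 = 33% to 10/20 = 50% of all LPs.
- If it does: 5 uncovered, all in the Table 2 arm, which is 5/30 = 17% to 5/20 = 25%.

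**Step 4. Illustration.** The event rate per LP, p, is an assumption. Expected events = n × p. Chance of at least one = 1 − (1 − p)^n, treating LPs as independent. For example, with p = 0.10: 1 − 0.90^10 = 1 − 0.349 = 0.651, and 1 − 0.90^5 = 1 − 0.590 = 0.410.

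| Assumed p | Expected, n = 10 | At least one, n = 10 | Expected, n = 5 | At least one, n = 5 |
|---|---|---|---|---|
| 2% | 0.2 | 18% | 0.1 | 10% |
| 5% | 0.5 | 40% | 0.25 | 23% |
| 10% | 1 | 65% | 0.5 | 41% |
| 20% | 2 | 89% | 1 | 67% |
| 30% | 3 | 97% | 1.5 | 83% |

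These are events that would occur with no scheduled main-phase enquiry after them. The number missed would be smaller by whatever share is reported spontaneously or found at Visit 12.

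**The case against.** The best defence is that silence in these lists proves little. The lists for Midpoint Visit b and End of Study Visit b also omit the blood draw that Section 4.1 calls for and both tables mark. The tables in turn show no telephone or AE mark at 1b, although the text requires a call there. The part of the protocol between Sections 4.4 and 6 was not available for this check and might hold follow-up wording. These points lower confidence in any single blank. They do not remove the finding at 11b, because the visit text and both tables agree on the order: AE review at visit a, puncture at visit b. Wording elsewhere would still have to be brought into line with them.

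Three stronger readings are tempting, and the documents do not support them.

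- *A reader might infer that AEs are sought only after the screening LP.* They are sought at 2b, weekly, at the midpoint and at 11a, and the midpoint LP has an AE assessment the following study week.
- *A reader might infer that the primary safety outcome is under-counted.* No event rate is given, and spontaneous reports or Visit 12, open to all completers, could recover events. Section 1 names feasibility and tolerability as the primary outcomes, and LP complications are procedure events rather than Flicker events. They still fall within Aim 1's undertaking to record any AE.
- *A reader might infer that events are missed unequally between arms.* That rests on one telephone cell at 11b. In Table 2 the 11b mark sits one row higher, under in-home therapy, so a slipped row cannot be excluded. If Table 1's contact does ask about AEs, the uncovered number is about 5, not 10; if it does not, no difference in AE ascertainment is shown. A count of 10 and an arm difference cannot both be claimed.

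Two side points fall away. A participant with banked CSF has no study screening LP to follow up, so the waiver adds no separate defect. The optional LP at 15b is already followed by an AE call at Visit 16.

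**Conclusion.** The point holds in a narrow form. The prompt contact is specified for the screening LP alone, and the final LP has no AE assessment marked after it in the main phase. Events after that LP may be missed in participants who do not go on to the extension, which is optional and needs fresh consent. About 5 or 10 final LPs are affected, depending on what the 11b telephone contact in Table 1 covers. This assumes that all 10 participants reach 11b. Any number of missed events is an assumption. At midpoint the gap is one of promptness only.

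The in-home therapy mark at 11b in Table 2, if intended, would mean that some device exposure also falls after the last AE review in that arm. The documents do not settle whether it is intended. This is an inexpensive correction to safety ascertainment; it does not affect the sample size.

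**What to change.** 1. Carry the day-after-LP AE contact already written for Screening Visit 1b over to Midpoint Visit b and End of Study Visit b.
2. Add a post-LP AE entry after 11b in both Table 1 and Table 2.
3. Reconcile the 11b telephone and in-home therapy cells of the two tables, and state whether the telephone contact includes AE questions.

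Per participant with three LPs, those followed by a main-phase AE assessment rise from 2 of 3 to 3 of 3, and those with a day-after contact from 1 of 3 to 3 of 3. The cost is wording and table edits plus at most 10 × 2 = 20 short calls, with no added clinic visit.

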#### Baseline Visit 2a:

• PET scan (florbetapir)

#### **Baseline Visit 2b:**

- Interim history review
- Medication review
- Adverse event review
- Confirm continued eligibility
- Vital signs, height & weight
- Physical and neurologic exams
- Cognitive testing/Questionnaires
  - Category Fluency (Animals)
  - o Benson
  - Trails A & B
  - Boston Naming Test (30 item)
  - Clinical Dementia Rating (CDR)
  - Neuropsychiatric Inventory (NPI)
  - Activities of Daily Living (FAQ)
- EEG
  - Flicker entrainment with exposure titration
  - EEG evaluation and induced activity
- Eye tracking task
- Randomization
  - Assigned to Flicker for 1st 4-weeks or 2nd 4-weeks
- Instructions for at-home Flicker sessions
  - Daily journal

**8.4 Study Visits.** Study visits at Emory may take place on more than 1 day to accommodate all the scheduled procedures (e.g., Visit 1 may be 2 days)

**Week 1** (Flicker administration [will start in study week 4 for half of participants and procedures will be identical to those followed for the Flicker/Flicker group])

- Days 1 -7
  - In-home therapy
  - Telephone call/email contact
    - Assessment of adverse events

- Answer any questions
- Remote adherence monitoring
  - If session has not been completed by 2:00 pm, reminder call is placed
- Day 3, 4 or 5
  - In-home Observation visit

#### **Weeks 2 – 4**(Days 15 - 28)

- In-home therapy
- Telephone call/email contact
  - Assessment of adverse events
  - Answer any questions
- Remote adherence monitoring
  - If session has not been completed by 2:00 pm, reminder call is placed
- Flicker administration will continue until all assessments have been completed.

## Midpoint Visit a:

- Interim history review
- Medication review
- Adverse event review
- Confirm continued eligibility
- Vital signs, height & weight
- Physical and neurologic exams
- Retinal Imaging
- PET scan (florbetapir)
- Cognitive testing/Questionnaires
  - Clinical Dementia Rating (CDR)
  - Neuropsychiatric Inventory (NPI)
  - Activities of Daily Living (FAQ)
- EEG
  - Flicker entrainment with exposure titration
  - EEG evaluation and induced activity
- Eye tracking task
- Instructions for at-home Flicker sessions (for those initiating Flicker)
  - Daily journal

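### At midpoint, clinic flicker and the blood-flow scan have no fixed order or recorded interval, so the acute part of the only randomised flicker versus no-flicker blood-flow difference (Aim 2) could be reduced

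*Combined protocol and SAP*

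**What the plan says.** Aim 2 (Section 2.2) asks whether flicker raises blood flow. Section 10.5 measures this by ASL MRI. Ten participants are randomised 1:1 (Sections 4.1 and 7.5) to flicker for 8 weeks or for the second 4 weeks only.

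- **Clinic flicker.** Section 8.4, Midpoint Visit a, lists EEG with "Flicker entrainment with exposure titration" and does not restrict it to one arm. The same list does restrict the home-session instructions to those who are starting. Section 10.2 confirms that the device is used during the EEG session. Tables 1 and 2 also mark tolerance testing on that day (6a and 7a).
- **Scan.** Section 8.4 lists the MRI under "Midpoint Visit b". Footnote 3 of Table 1 reads "MRI will occur on either study visit 6a or 6b", and footnote 3 of Table 2 reads "MRI will occur on either study visit 7a or 7b". Footnote 1 of each table makes this a two-day visit. Footnote 4 allows several days.
- **Early arm's home sessions.** Section 8.4, Weeks 2-4: "Flicker administration will continue until all assessments have been completed". Table 2 marks home therapy at 7a and 7b. No clock time is set. The nearest thing is "If session has not been completed by 2:00 pm, reminder call is placed".
- **Delayed arm's start.** Sections 4.1 and 8.4 (Week 1) start its flicker in week 4, and Midpoint Visit a gives the instructions. Table 1 puts training at 6b and home therapy from visit 7, in week 5.

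**The concern.** From midpoint onward both arms receive flicker, so the midpoint scan is the only randomised comparison of daily flicker with none. Section 1 reports, from preliminary preclinical work, that vessels stay dilated after stimulation stops, with diameter up 33% one hour later. An effect of that kind in the delayed arm at its midpoint scan would shrink the difference that Aim 2 needs.

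There are two ways this can happen under the current text. A participant can be scanned at 6a after the EEG on the same day. Or a home session can precede a 6b scan, if home flicker starts in week 4 after instruction at visit a. Neither can be recognised afterwards, because the interval is not recorded. What is at stake is how the blood-flow pilot data are read when the next trial is planned.

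**Working it through.** The documents give no effect size, SD or planned test for blood flow, so there is no figure to reproduce. The check covers time from last flicker to scan, then what that does to the contrast.

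**1. Time from last flicker to midpoint ASL**

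| Arm and situation | Interval | Basis |
|---|---|---|
| Delayed, scan at 6a after the EEG | same day | footnote 3, Table 1 |
| Delayed, scan at 6b, no home session yet | about 1 day | assumes consecutive days; footnote 4 allows longer |
| Delayed, scan at 6b, home flicker already started | under 1 day possible | Sections 4.1 and 8.4 as against Table 1 |
| Delayed, scan before the EEG at 6a | at least 3 x 7 = 21 days | last flicker at visit 2b, then study weeks 1-3; assumes no home session before 6a |
| Early, ongoing daily 1-hour sessions | 0 to 24 - 1 = about 23 hours | assumes the same time each day and none missed |

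Under the current text the intervals in the two arms can overlap. With the scan first, they do not.

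**2. Effect on the contrast**

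Let S be the sustained effect of daily flicker and A the acute effect of a recent session. Let gE and gD be the fractions of A still present at the scan in the early and delayed arms. Then

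early minus delayed = (S + gE x A) - (gD x A) = S + (gE - gD) x A.

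Scale so that S + A = 1, and let a be the acute share. The contrast is then (1 - a) + a x (gE - gD). None of a, gE or gD is in the documents, so the table shows a range.

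| Situation at the scan | a = 0.25 | a = 0.50 | a = 0.75 | a = 1 |
|---|---|---|---|---|
| Acute effect in early arm only (gE = 1, gD = 0) | 1.00 | 1.00 | 1.00 | 1.00 |
| Half present in delayed arm (gE = 1, gD = 0.5) | 0.875 | 0.75 | 0.625 | 0.50 |
| Equal in both arms (gE = gD) | 0.75 | 0.50 | 0.25 | 0 |
| Delayed arm only (gE = 0, gD = 1) | 0.50 | 0 | -0.50 | -1 |

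Worked case: with a = 0.5, gE = 1 and gD = 0.5, the contrast is 0.5 + 0.5 x 0.5 = 0.75.

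The acute part cancels fully only when gE = gD, and what remains is then S, unbiased. If gE and gD are unknown, the reader cannot tell which row applies.

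**3. Could analysis sort this out later?**

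With 5 per arm, the 95% confidence interval for a mean difference has half-width t(0.975, 8 df) x sqrt(2/5) = 2.306 x 0.632 = 1.46 SD. That is too wide to adjust for interval or to split the effect into two parts.

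**The case against.** A reader might infer that the acute effect would be lost at any midpoint scan. The documents do not support this. The only persistence figure is one hour, in preclinical work. For a scan at 6b on a later day, with no home session yet, the effect of the 6a EEG may well have faded while the early arm goes on with daily sessions. That is the first row of the second table, where nothing is lost. Placing the MRI at visit b, as Section 8.4 does, may even protect the contrast. For the same reason, carry-over to the lumbar puncture and blood draw at visit b is not shown.

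A reader might also infer that the sustained effect is biased. It is not if the acute effect is equal in both arms, and clinic flicker is scheduled in both.

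Two further objections carry weight. Aim 2 names no time point or arm contrast, and does not say whether its target is acute or sustained, so the midpoint contrast is implied by the design rather than specified. And scanning first does not isolate the sustained effect, because the early arm may have had a home session that day.

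What remains is narrower: same-day scanning after the EEG is permitted, the text and Table 1 disagree on when delayed-arm home sessions begin, and the interval is neither fixed nor recorded. Section 5 was not in the text available to me. If it sets an order or an interval, the point falls away to that extent.

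**Conclusion.** The point holds in a limited form. In the delayed-start arm, a same-day scan after the flicker EEG, or a scan after a home session if those start in week 4, could reduce the acute part of the midpoint blood-flow difference. The size cannot be computed from the documents. With an assumed acute share of one half, the contrast would keep between 100% and 0% of the full effect across the situations tabulated, and 50% if the acute effect is equal in both arms. This rests on an acute effect in humans that lasts long enough to reach the scan, which the documents suggest only from preclinical data.

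Severity is minor. Section 1 calls blood flow exploratory and Section 4.1 lists ASL among the secondary objectives. The study is declared not powered for generalizable results, and the primary feasibility and tolerability aims are untouched.

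**What to change.** 1. At midpoint, in both arms, do the MRI with ASL before the flicker EEG and tolerance testing. Footnote 3 of each table already allows visit 6a/7a; bring the Section 8.4 visit lists into line. The lumbar puncture and blood draw can stay at visit b.
2. Use the same order when MRI and flicker EEG share screening visit 1a. Section 8.2 lists both there without an order, and baseline and midpoint scans should be comparable.
3. Record the time from last flicker, home or clinic, to each ASL scan in both arms, and report it with the ASL results. At 5 per arm it can describe the data but not adjust them.
4. State that the midpoint contrast is then ongoing daily flicker versus none, including any acute effect of the early arm's last session, and that it does not separate acute from sustained effects.
5. Reconcile Sections 4.1 and 8.4 with Table 1 on when the delayed arm's training and home sessions start relative to the 6b scan.

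The cost is small: no added procedure, one order within a visit and one recorded time. Midpoint scheduling becomes slightly tighter, because the EEG session can last up to 3 hours (Section 10.2). MRI and EEG already share a visit at week 9 (End-of-study Visit a). The order there is also unstated and may differ from midpoint, but both arms are by then exposed and the recorded time will show any difference. Retinal imaging is at Midpoint Visit a in Section 8.4 and at 6b/7b in the tables. That is a separate clerical item.
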